### 7.7.2. Efficacy analysis

Efficacy analysis will be performed on an intent-to-treat basis. It will be analyzed for all patients entering this study, who received at least 1 dose of Xeljanz according to the local product document, and are available for an efficacy assessment performed after 6 months of treatment, or based on the last assessment performed at the time of treatment discontinuation if the patient dose not complete 6 months of treatment.

Analysis with effectiveness of treatment based on change from baseline in DAS28, after a treatment EULAR response and after a treatment ACR20 response. Evaluation of overall

assessment including 'Improve', 'Changeless', 'Aggravated' - based on each test results and clinical judgment analysis. As a result of evaluation, 'Without any assessment' remains with not available effectiveness result. 'Improve', 'Changeless', 'Aggravated' remain with available effectiveness. Overall assessment evaluation conclude with 'Improve' that Xeljanz is effective. Overall assessment evaluation conclude with 'Changeless' or 'Aggravated' that Xeljanz is less effective.

CCI

If the patient discontinues prematurely without completing the 6 months treatment, the reason of discontinuation will be analyzed.

### **7.8. Quality control**

Quality assurance audits will be performed at study centers by Pfizer's own independent quality assurance group or by the clinical research organization. These audits will be conducted according to Pfizer's procedures and the guidelines for Good Pharmacoepidemiology Practices (GPP) (see [Section 8.5](#)).

### **7.9. Limitations of the research methods**

This is a non-interventional PMS study conducted in the Republic of Korea to satisfy the requirements of MFDS: The protocol is determined by regulation of MFDS and not the specific disease and drug characteristics. The observational, non-controlled, and non-randomized design of this study has intrinsic limitations.

### **7.10. Other aspects**

Not applicable.

## **8. PROTECTION OF HUMAN SUBJECTS**

### **8.1. Patient information**

All parties will comply with all applicable laws, including laws regarding the implementation of organizational and technical measures to ensure protection of patient personal data. Such measures will include omitting patient names or other directly identifiable data in any reports, publications, or other disclosures, except where required by applicable laws.

The personal data will be stored at the study site in encrypted electronic form and will be password protected to ensure that only authorized study staffs have access. The study site will implement appropriate technical and organizational measures to ensure that the personal data can be recovered in the event of disaster. In the event of a potential personal data breach, the study site shall be responsible for determining whether a personal data breach has in fact occurred and, if so, providing breach notifications as required by law.

To protect the rights and freedoms of natural persons with regard to the processing of personal data, when study data are compiled for transfer to Pfizer and other authorized parties, patient

names will be removed and will be replaced by a single, specific, numerical code, based on a numbering system defined by Pfizer. All other identifiable data transferred to Pfizer or other authorized parties will be identified by this single, patient-specific code. The investigator site will maintain a confidential list of patients who participated in the study, linking each patient's numerical code to his or her actual identity. In case of data transfer, Pfizer will maintain high standards of confidentiality and protection of patients' personal data consistent with the clinical study agreement and applicable privacy laws.

## **8.2. Patient consent**

The informed consent documents and any patient recruitment materials must be in compliance with local regulatory requirements and legal requirements, including applicable privacy laws.

The informed consent documents used during the informed consent process and any patient recruitment materials must be reviewed and approved by Pfizer, approved by the institutional review board (IRB)/independent ethics committee (IEC) before use, and available for inspection.

The investigator must ensure that each study patient, or his/her legally acceptable representative is fully informed about the nature and objectives of the study the sharing of data relating to the study and possible risks associated with participation, including the risks associated with the processing of the patient's personal data. The investigator, or a person designated by the investigator, will obtain the written data privacy statement from each patient or the patient's legally acceptable representative before any study-specific activity is performed. The investigator will retain the original of each patient's signed data privacy statement. The investigator further must ensure that each study patient or his or her legally acceptable representative, or parent(s) is fully informed about his or her right to access and correct his or her personal data and to withdraw consent for the processing of his or her personal data.

Whenever consent is obtained from a patient's legally acceptable representative/parent(s), the patient's assent (affirmative agreement) must subsequently be obtained when the patient has the capacity to provide assent, as determined by the IRB/IEC. If the investigator determines that a patient's decisional capacity is so limited that he or she cannot reasonably be consulted, then, as permitted by the IRB/IEC and consistent with local regulatory and legal requirements, the patient's assent may be waived with source documentation of the reason assent was not obtained. If the study patient does not provide his or her own consent, the source documents must record why the patient did not provide consent (e.g., minor, decisionally impaired adult), how the investigator determined that the person signing the consent was the patient's legally acceptable representative, the consent signer's relationship to the study patient (e.g., parent, spouse), and that the patient's assent was obtained or waived. If assent is obtained verbally, it must be documented in the source documents.

## **8.3. Patient withdrawal**

Patients may withdraw from the study at any time at their own request, or they may be withdrawn at any time at the discretion of the investigator or Pfizer for safety, behavioral, or

administrative reasons. In any circumstance, every effort should be made to document the patient outcome, if possible. The investigator should inquire about the reason for withdrawal and follow-up with the patient regarding any unresolved AEs.

If the patient withdraws from the study, and also withdraws consent for disclosure of future information, no further evaluations should be performed, and no additional data should be collected. The sponsor may retain and continue to use any data collected before such withdrawal of consent.

#### **8.4. Institutional Review Board (IRB)/Independent Ethics Committee (IEC)**

The study protocol will be submitted to MFDS prior to the study. The ethical consideration on this study will be evaluated by the IRB/ IEC in each clinical site prior to the study, if the site has an approval process for this PMS study according to the local standard operation procedure of the site.

It is the responsibility of the investigator to have prospective approval of the study protocol, protocol amendments, and informed consent forms, and other relevant documents (e.g., recruitment advertisements), if applicable, from the IRB/IEC. All correspondence with the IRB/IEC should be retained by the investigator. Copies of IRB/IEC approvals should be forwarded to Pfizer.

#### **8.5. Ethical conduct of the study**

The study will be conducted in accordance with legal and regulatory requirements, as well as with scientific purpose, value and rigor and follow generally accepted research practices described in Guidelines for GPP issued by the International Society for Pharmacoepidemiology (ISPE), Good Epidemiological Practice (GEP) guidelines issued by the International Epidemiological Association (IEA), Pharmaceutical Research and Manufacturers Association (PhRMA) guidelines, and Korea PMS regulations and/or guidelines.

### **9. MANAGEMENT AND REPORTING OF ADVERSE EVENTS/ADVERSE REACTIONS**

#### **9.1. Requirements**

The table below summarizes the requirements for recording safety events on the CRF and for reporting safety events on the non-interventional study (NIS) adverse event monitoring (AEM) Report Form to Pfizer Safety. These requirements are delineated for three types of events: (1) SAEs; (2) non-serious AEs (as applicable); and (3) scenarios involving drug exposure, including exposure during pregnancy, exposure during breast feeding, medication error, overdose, misuse, extravasation, and occupational exposure. These events are defined in [Section 9.4](#).

Safety event	Recorded on the CRF	Reported on the NIS AEM Report Form to Pfizer Safety within 24 hours of awareness
SAE	All	All
Non-serious AE	All	None

Safety event	Recorded on the CRF	Reported on the NIS AEM Report Form to Pfizer Safety within 24 hours of awareness
Scenarios involving exposure to a drug under study, including exposure during pregnancy, exposure during breast feeding, medication error, overdose, misuse, extravasation; lack of efficacy; and occupational exposure	All (regardless of whether associated with an AE), except occupational exposure	All (regardless of whether associated with an AE)

For each AE, the investigator must pursue and obtain information adequate both to determine the outcome of the AE and to assess whether it meets the criteria for classification as a SAE (see section "Serious Adverse Events" below)

Safety events listed in the table above must be reported to Pfizer within 24 hours of awareness of the event by the investigator **regardless of whether the event is determined by the investigator to be related to a drug under study**. In particular, if the SAE is fatal or life-threatening, notification to Pfizer must be made immediately, irrespective of the extent of available event information. This timeframe also applies to additional new (follow-up) information on previously forwarded safety event reports. In the rare situation that the investigator does not become immediately aware of the occurrence of a safety event, the investigator must report the event within 24 hours after learning of it and document the time of his/her first awareness of the events.

For safety events that are considered serious or that are identified in the far right column of the table above that are reportable to Pfizer within 24 hours of awareness, the investigator is obligated to pursue and to provide any additional information to Pfizer in accordance with this 24-hour timeframe. In addition, an investigator may be requested by Pfizer to obtain specific follow-up information in an expedited fashion. This information is more detailed than that recorded on the CRF. In general, this will include a description of the AE in sufficient detail to allow for a complete medical assessment of the case and independent determination of possible causality. Any information relevant to the event, such as concomitant medications and illnesses must be provided. In the case of a patient death, a summary of available autopsy findings must be submitted as soon as possible to Pfizer or its designated representative.

## 9.2. Reporting period

For each patient, the safety event reporting period begins at the time of the patient's first dose of Xeljanz or the time of the patient's data privacy statement if s/he is already exposed to Xeljanz, and lasts through the end of the observation period of the study which must include at least 28 calendar days following the last administration of Xeljanz; a report must be submitted to Pfizer Safety (or its designated representative) for any of the types of safety events listed in the table above occurring during this period. If a patient was administered a drug under study on the last day of the observation period, then the reporting period should be extended for 28 calendar days following the end of observation.

Most often, the date of data privacy statement is the same as the date of enrollment. In some situations, there may be a lag between the dates of data privacy statement and enrollment. In these instances, if a patient provides data privacy statement but is never enrolled in the study (eg, patient changes his/her mind about participation), the reporting period ends on the date of the decision to not enroll the patient.

If the investigator becomes aware of a SAE occurring at any time after completion of the study and s/he considers the SAE to be related to Xeljanz, the SAE must also be reported to Pfizer Safety.

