## 7. RESEARCH METHODS

### 7.1. Study design

This is an open-label, non-comparative, non-interventional, prospective, and multi-center study conducted in Korean health care centers by accredited physicians (ie, investigators). The study population will be adult patients with moderately to severely active RA who have had an inadequate response or intolerance to methotrexate. Xeljanz will be administered according to the “Dosage and Administration” of the approved labeling. There is no visit or activity mandated by this study. The investigator will collect patient data and record the information on each patient’s case report form (CRF).

CCI

Also, investigators collect data on the Xeljanz retrospectively from the subjects who have been administered the Xeljanz according to the local product documents but not participated in this study until 26 June 2022.

Safety is the primary interest of this study, which will be assessed based on adverse events (AEs) that occur during the 6 months from the first dose of Xeljanz. The efficacy endpoints will be the modified Disease Activity Score using 28 joint counts (DAS28) change from baseline, [European League Against Rheumatism](#) (EULAR) response, and American College of Rheumatology 20% improvement criteria (ACR20) response after treatment (see [Section 7.3](#)).

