### 7.2.5. Study procedures

The investigator should enroll all patients to whom Xeljanz is prescribed for the first time according to the local product document and who agree to participate in this study by signing the data privacy statement (used in place of the informed consent form) by continuous registration method. In case of the patients who already have been administered Xeljanz but not participated in this study, study related information from the first administration until the last day of the observation period should be collected retrospectively. Xeljanz tablets will be medicated by the investigator's prescription under usual clinical practice. Pfizer Korea will not provide the medicinal product for this study.

There will be no mandatory visit during the study. The investigators will collect relevant data from the time of initiating administration of Xeljanz until 6 months of treatment. If the patient does not complete 6 months of treatment, relevant data should be collected based on the last assessment performed at the time of treatment discontinuation. The investigator should record the following information on the patient's CRF:

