### **7.3. Variables**

#### **7.3.1. Safety variables**

Safety will be assessed by the investigator based on AEs that occur during 6 months from the first treatment for all patients who have received at least 1 dose of Xeljanz according to the local product document.

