##### **7.3.1.1. Adverse events**

Please refer to [Section 9](#) for the definition of non-serious and serious adverse events (SAEs).

Any AEs observed and reported within the reporting period will be recorded on the CRF by the investigator, regardless of the causal relationship with Xeljanz (see [Section 9.2](#)). The AEs can be reported by the patients. The investigator will also collect AE data by asking the patient questions such as “Have you had any health problem since the last visit?”

Check either “yes” or “no” in the AE section of CRF. If “yes”, record the following information:

Event name: Record the name of the AE according to the Korean Version of World Health Organization - Adverse Reaction Terminology (WHO-ART) distributed by Korean Ministry of Health and Welfare. If there is no not an appropriate term in the WHO-ART, record the name of the AE according to the Medical Terminology Dictionary written by the Korean Medical Society. If possible, specify diagnosis, not individual symptoms.

Date of onset: Record the onset date of the AE. Record approximate date if an actual date is unknown.

Date of recovery: Record the stop date of the AE if the outcome of the AE is recovered or recovered with sequelae (see below). Record approximate date if an actual date is unknown.

Seriousness: Check either “yes” or “no” to indicate if the event is a SAE. If “yes” record appropriate category of the seriousness (see [Section 9](#) for the definition and reporting of SAEs).

**Severity:** Evaluation of AE severity must be done according to the following categories:

- Mild: Not causing any significant problem to the patient. Administration of medicinal product continues without dose adjustment.
- Moderate: Causes a problem that does not interfere significantly with usual activities or the clinical status. Dose of the medicinal product is adjusted or other therapy is added due to the AE.
- Severe: Causes a problem that interferes significantly with usual activities or the clinical status. The medicinal product is stopped due to the AE.

If the severity of an AE changes, the AE must be entered separately. Record the stop date of the previous severity and onset date of the new severity – along with completion of all other related items.

**Causality assessment:** The causal relationship of AEs to the medicinal product must be allocated by the investigator according to the following criteria in alignment with the requirements of MFDS:

- Certain

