4.4. Safety Endpoints

The incidence and number with 95% confidence interval for all adverse events/adverse drug reactions investigated within 6 months from initial dosing after at least 1 dose of Xeljanz® during the study.

- Seriousness
- Severity
- Causality assessment
- Action taken
- Outcome

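### For patients already on the drug, Protocol 7.3.1.1 ties CRF recording of AEs to a period that 9.2 starts at the privacy statement, while 7.2.5 and the safety endpoint start at first dose

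*Protocol*

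**What the plan says.** **Start at the privacy statement.** Protocol 9.2 starts the reporting period at first dose, or at the patient's "data privacy statement if s/he is already exposed to Xeljanz, and lasts through the end of the observation period of the study". Protocol 7.3.1.1 carries this period into the CRF: "Any AEs observed and reported within the reporting period will be recorded on the CRF by the investigator". The same sentence ends with a reference to 9.2.

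**Start at first dose.** Protocol 7.2.5 has two groups. For prospective patients, "The investigator should enroll all patients to whom Xeljanz is prescribed for the first time". The retrospective group is "the patients who already have been administered Xeljanz but not participated in this study", and for them "study related information from the first administration until the last day of the observation period should be collected retrospectively". The safety window makes no exception for this group:
- Protocol 7.1: safety is "assessed based on adverse events (AEs) that occur during the 6 months from the first dose of Xeljanz".
- Protocol 7.3.1: the basis is "AEs that occur during 6 months from the first treatment for all patients who have received at least 1 dose of Xeljanz".
- SAP 4.4: the endpoint covers "all adverse events/adverse drug reactions investigated within 6 months from initial dosing".

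**Waiver.** Protocol 7.2.1 and 7.2.5.1 let the IRB/IEC decide whether consent or the privacy statement is needed for retrospective patients, so some may have no statement date.

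**The concern.** Retrospective patients are by definition already exposed, so the second branch of the 9.2 start rule fits them. A prospective patient who signs after the first dose would also fall under it. For these patients the protocol gives sites two different starting points for the AE page of the CRF.

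If a site uses the later one, AEs between first dose and signature may not reach the database. The patient can still count in the denominator, because SAP 3.1 asks only for one dose according to the local product document and an assessment of safety information. The error runs one way: incidence comes out too low. AE incidence is the study's primary interest (Protocol 7.7.1). The exposure is clearest in the RMP report, which draws on prospective and retrospective data (Protocol 7.2.3, SAP 2.2.2).

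**Working it through.** The plan gives no figure to reproduce on this point. The check is a comparison of the texts, followed by an illustration of scale.

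**1. Start dates for an already-exposed patient**

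| Place | Governs | Start |
|---|---|---|
| Protocol 9.2 | safety event reporting period | privacy statement; none if waived |
| Protocol 7.3.1.1 | CRF recording of AEs | as 9.2, by cross-reference |
| Protocol 9.1 table | CRF recording and safety reports | all AEs on the CRF; no start date |
| Protocol 7.2.5 | retrospective data collection | first administration |
| Protocol 7.1, 7.3.1 | safety assessment | first dose |
| SAP 4.4 | safety endpoint | initial dosing |

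No visible passage says which start governs the CRF. Read literally, the 9.2 period of a patient who signs 6 months or more after first dose does not overlap the analysis window at all.

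**2. One patient, late start applied.** Assume a constant AE hazard, a true 6-month incidence p, signature at month m, and loss of every AE with onset before signature. Recorded probability = 1 − (1 − p)^((6 − m)/6), and 0 for m ≥ 6. With p = 30% this gives 25.7% (m = 1), 16.3% (m = 3), 5.8% (m = 5) and 0% (m ≥ 6).

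**3. A whole report.** Let r be the retrospective share of patients, s the share of those at sites that apply 9.2 to the CRF, and g the fraction of their patients with an in-window AE for whom none is recorded. If true incidence is the same in both modes:

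recorded incidence = p(1 − r·s·g), so relative shortfall = r·s·g.

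If statements are signed uniformly over the 6 months, put h = −ln(1 − p). The probability of at least one recorded AE is then 1 − p/h, and g = 1 − (1 − p/h)/p. For p = 30%: h = 0.357, 1 − p/h = 0.159, g = 1 − 0.159/0.30 = 0.47. For p = 20% and 40%, g = 0.48 and 0.46. If all sign after month 6, g = 1.

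| r | shortfall, s = 10%, g = 0.47 | shortfall, s = 10%, g = 1 | s for a 5% shortfall, g = 0.47 | s for a 5% shortfall, g = 1 |
|---|---|---|---|---|
| 10% | 0.5% | 1% | not reachable (0.05/0.047 > 1) | 50% |
| 30% | 1.4% | 3% | 35% | 17% |
| 50% | 2.4% | 5% | 21% | 10% |

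Example: r = 30%, s = 10%, g = 0.47 gives 0.30 × 0.10 × 0.47 = 1.4%, so 30% would be recorded as about 29.6%.

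The documents give none of p, r, s or g, and the 5% marker is only a convenient reference. Both values of g are on the high side. Protocol 7.3.1.1 refers to when AEs are observed and reported, not to onset, so an AE still present at signature, or first reported later, could be recorded even under 9.2.

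**The case against.** The case for leaving the text alone is substantial.

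- **Purpose of 9.2.** Its sentence goes on to require reports to the sponsor's safety group, and the 9.1 table treats CRF recording separately, with no start date. This makes it plausible that 9.2 governs only safety reports. It does not settle the matter: 9.2 does not say that its period is limited to such reports, Section 9.1 covers CRF recording as well, and 7.3.1.1 itself sends the person filling in the CRF to 9.2.
- **No prohibition.** Protocol 7.3.1.1 does not forbid recording earlier AEs, and 7.2.5 is the more specific rule for retrospective patients. A site that records from first dose complies with every passage. This stands, and it is why loss of AEs is a risk and not a consequence of the plan.
- **Practicality.** For late signers, or under a waiver, the literal 9.2 rule would leave a chart review with almost nothing to record. A site would probably notice, which makes the g = 1 case less likely.
- **Denominator.** A patient whose window was never assessed arguably fails SAP 3.1. But SAP 3.1 has no exclusion for a patient whose AE record merely starts late.
- **Blacked-out text.** The observation period has no visible definition, and redacted parts of Protocol 7.1 and 7.2.3 and SAP 2.2 may bear on it.

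A reader might infer that the protocol orders sites to drop AEs before the statement, or that the reported incidence is known to be biased. The documents support neither: they show two unreconciled instructions and nothing on which one sites used.

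**Conclusion.** The conflict between instructions is real, and it concerns only the start of CRF recording for already-exposed patients, chiefly the retrospective group. If a site follows the 7.3.1.1 cross-reference, AE incidence is biased downward. If it follows 7.2.5, there is no bias.

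The size cannot be determined from the documents. It is likely small, because the shortfall is a product of three fractions. With a tenth of retrospective patients at sites applying 9.2, it is 0.5% to 5% in relative terms across the assumed range. It becomes material only if retrospective patients make up much of the report and many sites take the late start. These figures assume equal true incidence in both modes and tend to overstate the loss.

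A reader might extend the point to the re-examination report, since 7.7.1 defines the primary interest over that period. No effect there is shown: the documents do not say how many retrospective patients that report contains. The RMP report is the clear case. This is a minor fix, worth making because the error would run in one direction and the remedy is a sentence.

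**What to change.** **Protocol 7.3.1.1.** State that for retrospectively collected patients all AEs from first dose through the 6-month window are recorded on the CRF, whatever the date or waiver of the privacy statement, and that the 9.2 start date does not limit CRF recording. This matches the window already used in Protocol 7.1, 7.2.5 and 7.3.1 and SAP 4.4.

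**Protocol 9.1 and 9.2.** Ask the sponsor to reconcile these sections on reports to its safety group of events that occurred before the statement, or in patients with a waiver. The rule is for the sponsor to set. The documents leave it open, and this review does not propose one.

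**Optional.** In any report that holds both collection modes, show AE incidence with its 95% confidence interval by mode beside the combined figure. This is a descriptive check. It cannot prove which rule sites used, because the modes may also differ in chart completeness and case mix.

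**Cost.** One clarifying sentence in 7.3.1.1, a sponsor decision on 9.1 and 9.2, and a note to sites. There are no new patients or visits. Recorded incidence may come out higher. The optional split needs a collection-mode flag, which SAP 4.1 does not list although the CRF instructions in 7.2.5.1 and 7.2.5.2 already differ by mode. The intervals by mode will be wider than the combined one.
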